### **8.5. OTHER SAFETY RELATED CLINICAL OUTCOMES**

The following clinical outcomes will be assessed:

- Death (from hepatic and non-hepatic related causes)
- Complications of portal hypertension including gastroesophageal bleeding, interventions to manage variceal bleeding (e.g., variceal banding/sclerotherapy or TIPS placement) and diuretic resistant ascites
- Complications of Cirrhosis: new-onset ascites, hepatic encephalopathy, hepatorenal syndrome (type I or II), and spontaneous bacterial peritonitis).
- Hospitalization

Each of these events including hospitalizations will be adjudicated by the site

investigator as expected as part of the natural history of moderately severe AH, or unexpected (e.g., suicide, motor vehicle accident, or myocardial infarction).

## **9. ADVERSE EVENTS**

### **9.1. DEFINITION OF ADVERSE EVENTS**

#### **9.1.1. Reporting Period for Adverse Events**

Safety will be assessed in terms of AEs. All AEs, whether observed by the investigator, reported by the subject, noted from laboratory findings, or identified by other means, will be recorded from Day 0 until the patient completes trial participation (D-180).

AEs are defined as any untoward medical occurrence associated with the use of the study medication in humans, whether or not considered related to study medication. An AE (also referred to as an adverse experience) can be any unfavorable and unintended sign (e.g., an abnormal laboratory finding), symptom, or disease temporally associated with any use of the study medication, without any judgment about causality and irrespective of route of administration, formulation, or dose, including an overdose. For this trial, study medication refers to double blind OCA or placebo in the DB phase.

AEs include, but are not limited to: (1) a worsening or change in nature, severity, or frequency of condition(s) present at the start of the trial; (2) subject deterioration due to primary illness; (3) intercurrent illness; and (4) drug interaction.

Subjects should be questioned in a general way, without leading the patient or asking about the occurrence of any specific symptom. The investigator should attempt to establish a diagnosis of the event based on signs, symptoms, and/or other clinical information. The diagnosis and not the individual signs/symptoms should be documented as the AE. For example, if the underlying disease process is a stroke, it would not be appropriate to record the AE by describing the symptoms “sudden numbness, dizziness, and difficulty speaking.” The AE medical term of “stroke or cerebrovascular accident” should be recorded as it more accurately describes the AE.

Following questioning and evaluation, all AEs, whether believed by the investigator to be related or unrelated to the study medication, must be documented in the subject’s medical records, in accordance with the investigator’s normal clinical practice and on the AE CRF. Each AE is to be evaluated for duration, intensity, frequency, seriousness, outcome, other actions taken, and relationship to the study medication.

##### **9.1.1.1. Pretreatment Event(s)**

Untoward events that occur during screening phase (prior to randomization) should be recorded as medical history.

### 9.1.2. Severity of AEs

AEs must be graded for severity (i.e., intensity). A severity category of mild, moderate, or severe, as defined in Table 2, must be entered on the AE CRF. It should be noted that the term “severe” used to grade intensity is not synonymous with the term “serious.” For example, severe headache is a severe AE, but may not be a serious AE. The assessment of severity is made regardless of study medication relationship or of the seriousness of the AE.

**Table 2      Severity of AEs**

Grade	Clinical Description of Severity
1 = Mild	Causing no limitation of usual activities; the subject may experience slight discomfort.
2 = Moderate	Causing some limitation of usual activities; the subject may experience annoying discomfort.
3 = Severe	Causing inability to carry out usual activities; the subject may experience intolerable discomfort or pain.

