### **1.2 CLINICAL EXPERIENCE WITH OBETICHOLIC ACID (OCA)**

#### **1.2.1 Phase 1**

OCA was administered orally in a single ascending dose trial (Protocol 747-101) and a multiple ascending dose trial (Protocol 747-102) to evaluate the safety, tolerability and pharmacokinetics (PK) of OCA, administered orally, in healthy volunteers. In Protocol 747-101, single doses of 50 to 500 mg of OCA were administered, while doses of 25 to 250 mg of OCA were administered once daily for 12 days in the multiple dose trial (747-102).

No AEs of clinical concern were seen in the single dose trial. In the multiple dose trial, clinically significant elevations in the aminotransferases were seen at the 250 mg dose. Minor aminotransferase increases of no clinical concern were seen at the 100 mg dose level. However, in the 250 mg dose group, 6 of 8 subjects who received OCA had increases in aminotransferase(s); 4 subjects had elevations in both ALT and AST, while 2 subjects had increased ALT only. These increased values were 3 to 5 times the ULN in some subjects and were considered to be dose limiting. The increases in hepatocellular enzymes are thought to be attributable to detergent effects seen with other bile acids like CDCA. It should be noted that this dose is more than 25 times higher than the doses that will be used in this trial.

OCA is rapidly and extensively conjugated with glycine and taurine. These conjugates are present in much greater concentrations than the parent drug, and are

equipotent FXR agonists to the parent drug. OCA has demonstrated dose proportional increases in  $C_{max}$  (50 - 500 mg range) and considerable enterohepatic circulation (lasting several days after the last dose was administered) was seen. Excretion is assumed to be primarily fecal, as is typical for a bile acid, and, at a low level, was recovered in the urine.

## 1.2.2 Phase 2 and Phase 3

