## 10. STATISTICAL METHODS

### 10.1. ANALYSIS SETS

Primary end point: Analysis will be based on intention-to-treat principle. We will evaluate the main outcome, change in MELD score at day 42, in the framework of the repeated measurements analysis of covariance (ANCOVA) model. Specifically, MELD score at each follow-up visit will be used as the outcome variable. The main predictor is treatment group (GROUP). We will adjust for time (visit) and baseline MELD score and include the interaction between GROUP and visit. The interaction term allows evaluation of GROUP difference at each visit. The main comparison is the differences of MELD score change at day # 28 between two groups. A random intercept will be used to adjust for the correlation among the observations from the same subject. We will also evaluate the GROUP difference at 90 and 180 days in the framework of above repeated ANCOVA model.

SAEs during treatment: The primary analysis is to compare the proportion of patients having at least one SAE during the treatment period between the two groups using Chi-square tests. *SAE during follow-up* will be analyzed similarly. Other safety outcomes include AEs, discontinuations, pre-defined laboratory abnormalities, and predefined EKG abnormalities. Other continuous outcomes will be analyzed in a similar way to MELD score, binary outcomes will be analyzed in a similar way to SAE, and censored time-to-event outcomes will be analyzed using appropriate survival analysis tools (e.g., Kaplan-Meier plots, Cox models).

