#### **10.3.1. AEs**

AEs will be labeled according to standard medical terminology using the case report forms provided. Summary tables of treatment-emergent AEs will be provided. A TEAE is any AE that newly appeared, increased in frequency, or worsened in severity following initiation of study medication. The incidence of TEAEs will be tabulated by system organ class and preferred term for each treatment group, and by severity and relationship to treatment. Tables of TEAEs leading to study medication discontinuation and SAEs will be provided.

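### Table 2 has no laboratory criterion, so a symptom-free liver-test rise can only be graded mild, and no categorical by-arm measure of liver-test severity is prespecified

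*Combined protocol and SAP*

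**What the plan says.** Section 9.1.1 defines an adverse event broadly. It "can be any unfavorable and unintended sign (e.g., an abnormal laboratory finding"), whether or not it is thought to be related to study medication.

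Section 9.1.2 makes one scale compulsory: "A severity category of mild, moderate, or severe, as defined in Table 2, must be entered on the AE CRF". It adds that severity is judged independently of seriousness and of relationship to the drug.

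Table 2 has three grades:

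- Mild: "Causing no limitation of usual activities; the subject may experience slight discomfort".
- Moderate: "Causing some limitation of usual activities; the subject may experience annoying discomfort".
- Severe: "Causing inability to carry out usual activities; the subject may experience intolerable discomfort or pain".

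Section 10.3.1 then tabulates the incidence of treatment-emergent events "for each treatment group, and by severity and relationship to treatment".

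For laboratory data as such, section 10.1 lists among the other safety outcomes "pre-defined laboratory abnormalities, and predefined EKG abnormalities". Section 10.3.2 plans descriptive statistics at each visit and change from the pretreatment value by arm.

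**The concern.** The scale measures what the patient feels and can do. That suits pruritus or nausea. It does not suit a rise in ALT, AST, bilirubin or creatinine that the patient cannot feel. Followed as written, Table 2 puts a slight rise and a very large one in the same grade, provided neither causes symptoms.

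This matters because the trial gives a bile acid derivative to patients with acute liver injury, so biochemical liver injury is something the safety tables should be able to show. A reader who takes the severity table at face value could conclude that laboratory events were mild, when the scale could not have returned any other answer for silent ones.

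**Working it through.** No figure in the plan bears on this point. The check is a reading of the rules against each other.

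**Step 1. Can a laboratory result enter the adverse-event tables?** Yes, under section 9.1.1. That section also asks for the diagnosis to be recorded in preference to individual signs. A rise recorded under a diagnosis is still an adverse event and is still graded by Table 2.

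**Step 2. Is another scale available for it?** No. Section 9.1.2 makes Table 2 mandatory, and no section gives a laboratory grading scale.

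**Step 3. Which grade does a symptom-free rise meet?**

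| Grade | What it needs | Met by a rise the patient does not feel? |
|---|---|---|
| Mild | No restriction; slight discomfort is possible but not required | Yes |
| Moderate | Some restriction | No |
| Severe | Inability to carry on as usual | No |

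The discomfort and pain wording does not alter this, because a silent rise causes neither. The size of the rise appears in no row.

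**Step 4. Does this reach a planned output?** Yes. Section 10.3.1 reports treatment-emergent events by arm and by severity, using these grades.

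**Step 5. Does another planned output classify the size of a liver-test rise by arm?**

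- Section 10.1 names laboratory abnormalities as an outcome but states no analyte, threshold or time window for them, and no other section does.
- Section 10.3.2 gives descriptive summaries by visit. It describes no threshold counts, no worst on-study value per patient and no shift table. Section 10.3.3, by contrast, does plan a percentage of patients with clinically significant ECG findings. Laboratory results have no counterpart.
- Section 8.3 requires follow-up of clinically significant abnormal values but attaches no number to that term.
- Criterion (f) of the SAE definition in section 9.2.1 can capture an important medical event. It rests on the investigator's judgement, has no laboratory cut-point, and by section 9.1.2 leaves the severity grade unchanged.
- MELD, Child-Pugh and Discriminant Function are assessed through treatment and follow-up (Table 1). They are composite scores and do not classify individual liver tests.

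**Result.** A silent laboratory event is mild by rule, and no prespecified analysis counts patients by degree of liver-test abnormality in each arm.

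**The case against.** The strongest reply is that liver harm has many routes to the reader outside Table 2. MELD at 6 weeks is a primary endpoint compared by arm. SAEs during treatment are the other primary endpoint. Mortality and discontinuations are secondary. Section 4.3.1 ties stopping of study medication to numeric worsening of MELD or Discriminant Function, and section 10.3.1 tabulates events that lead to discontinuation. Section 10.3.4 lists hepatic complications, and a safety committee reviews the data. All of this stands. It confines the loss to severity grading, but none of it supplies the missing classification of liver tests.

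Three stronger readings are tempting, and the documents do not support them.

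- **That the tables will hide a known toxicity of the trial treatment.** Section 1.2.1 says of aminotransferases: "These increased values were 3 to 5 times the ULN in some subjects and were considered to be dose limiting". That was at 250 mg daily in healthy volunteers, against 10 mg here (250 / 10 = 25-fold). At 10 mg, section 1.2.2.1 reports significant improvement in ALT and AST in one biliary cirrhosis trial. In the other, both fell without reaching significance. Understatement is a risk here and not an established result.
- **That the scale favours obeticholic acid.** The same scale applies to both arms under blinding. It can mask a difference in size between arms, but it does not lean towards either.
- **That a silent worsening of an abnormality present at Day 0 falls out of the treatment-emergent count because its severity stays mild.** This is a possible reading only. The definition in section 10.3.1 also admits events that are new or more frequent, and section 9.1.1 counts a change in the nature of an existing condition.

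One might also ask for separate grades for life-threatening and fatal events. That would add little, because seriousness, outcome and death are already recorded and reported on their own.

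Finally, descriptive statistics may include a standard deviation or a maximum, which could reveal outlying values. Section 10.3.2 does not say which statistics it means, and neither one gives a count of patients by degree of abnormality.

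**Conclusion.** The point holds in a limited form. Table 2 is compulsory, has no laboratory criterion, and places a symptom-free laboratory event of any size in the mild grade. The by-arm severity tables therefore cannot show how large a silent liver-test rise was and could understate biochemical liver injury in either arm. Because the abnormalities in section 10.1 are undefined and section 10.3.2 is descriptive only, no categorical by-arm measure of liver-test severity is prespecified.

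The effect cannot be put as a number, since the documents give no expected rate of silent liver-test rises at 10 mg in this population. It touches neither the primary MELD analysis, nor the SAE comparison, nor mortality, nor the laboratory values themselves. The conclusion assumes that investigators apply Table 2 as written. If some grade laboratory events by informal judgement, the tables would also mix two scales.

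The change should be made, because the remedy is specific and cheap. It is not a fault that threatens the trial's main conclusions.

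**What to change.** - Keep Table 2 for symptomatic events.
- State that laboratory adverse events are graded numerically. The data coordinating unit derives the grade from recorded results, using the highest on-study value as a multiple of the local ULN and, where the Day 0 value is already abnormal, as a multiple of that value too. The second multiple is needed because these patients enter with abnormal liver tests.
- Name the set of cut-points, published or written into the plan, and fix it before unblinding.
- Use these grades in the section 10.3.1 severity table and as the definition of the laboratory abnormalities in section 10.1. Add a by-arm table of each patient's worst shift from Day 0.
- Reconcile section 8.3, which has local laboratories run the tests, with section 10.3.2, which describes the data as central. The source of the ULN depends on this.

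The cost is protocol wording, entry of local ULNs and some programming. The blood is already drawn at every clinic visit in Table 1. The one drawback is that laboratory events will look more severe in both arms than they would under Table 2.

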### 9.1.3. Relationship of AEs to Study Medication

The investigator will document her/his opinion of the relationship of the AE to treatment with study medication using the criteria outlined in Table 3. An AE for which there is a ‘reasonable possibility’ that the study medication caused the AE is otherwise referred to as suspected adverse reaction (SAR). ‘Reasonable possibility’ means there is evidence to suggest a causal relationship between the study medication and the AE.

**Table 3 Relationship of AEs to Study Medication**

Relationship	Description
Definite	A reaction that follows a reasonable temporal sequence from administration of the drug or in which the study medication level has been established in body fluids or tissue; that follows a known or expected response pattern to the suspected drug; and that is confirmed by improvement on stopping or reducing the dosage of the study medication, and reappearance of the reaction on repeated exposure.
Probable	A reaction that follows a reasonable temporal sequence from administration of the study medication; that follows a known or expected response pattern to the suspected study medication; that is confirmed by stopping or reducing the dosage of the study medication; and that could not be reasonably explained by other factors.
Possible	A reaction that follows a reasonable temporal sequence from administration of the study medication; that follows a known or expected response pattern to the suspected study medication; but that could readily be produced by a number of other factors.
Unlikely	A reaction that does not follow a reasonable temporal sequence from administration of the study medication; that does not follow a known or suspected response pattern to the suspected study medication; and that could reasonably be explained by known characteristics of the subject's clinical state.
Not Related	Any event that does not meet the above criteria.

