**Table 4: Requirements for Reporting AEs to various stakeholders**

	Local IRB	NIAAA	DSMB	Other centers	Intercept	FDA
AEs	Continuing Review	Annual Report	Every 6 months	DSMB reports (every 6 months)	DSMB reports (every 6 months)	Annual Report
TEAEs	Continuing Review	Annual Report	Every 6 months	DSMB reports (every 6 months)	DSMB reports (every 6 months)	Annual Report
SAEs	Continuing Review	2 working days	Every 6 months	DSMB reports (every 6 months)	DSMB reports (every 6 months)	Annual Report
SUSAR	5 days	2 working days	2 working days	2 working days	2 working days	7 days if death 15 days if other
Fatality	If unrelated Follow SAE timeline If related follow SUSAR timeline					

AE: Adverse Event; TEACs: Treatment Emergent Adverse Event; SAE: Serious Adverse Event; SUSAR: Serious Unsuspected Adverse Reaction; DSMB: Data and Safety Monitoring Board

The study designated physician for TREAT 002 is [name].

Safety Officer for the DCU of the TREAT Consortium is [name].

All SAEs must be reported to the DCU (i.e., within 2 working days) after the investigator identifies the SAE. SAEs should be entered into the OnCore system within 2 working days of the investigator becoming aware of the event. An initial report by telephone should be followed as soon as possible by completion of the SAE CRF. Any supporting source documentation should be emailed to the assigned contact information as soon as possible. At a minimum the following information should be provided at the time of the initial report: 5-digit Study ID, a description of the event, at least one criterion classifying the event as Serious and the name and title of the reporting individual. Additionally, judgment of causality by the investigator must be provided as soon as possible to ensure timely reporting to regulatory authorities.

Following the initial report, any additional information obtained by the investigator about the SAE must be reported promptly to the DCU.

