### **9.4. FOLLOW UP OF AEs**

All AEs, including clinically significant laboratory values or physical examination findings relative to pretreatment assessments, must be followed during the trial until

the AE resolves, is no longer of clinical concern, has stabilized or is otherwise explained, or the patient is lost to follow up.

AEs ongoing at the final visit that are deemed to be ‘possibly, probably, or definitely’ related or of other clinical significance must be followed for as long as necessary to adequately evaluate the safety of the patient or until the event stabilizes, resolves, or is no longer of clinical concern. If resolved, a resolution date for the AE should be documented on the CRF. The investigator must ensure that follow up includes any supplemental investigations indicated to elucidate the nature and/or causality of the AE. This may include additional laboratory tests or investigations, or consultation with other healthcare professionals, as considered clinically appropriate by the investigator.

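### Table 3 makes a known or expected response pattern a condition of every related grade, so the site must grade a novel reaction with plausible timing as Not Related, contrary to sections 9.1.3 and 9.2.2

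*Combined protocol and SAP*

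**What the plan says.** Section 9.1.3 tells the investigator to record the relationship of each AE to study medication on the five-grade scale in Table 3. The pattern condition stands in all three related rows:

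- **Definite:** a reaction "that follows a known or expected response pattern to the suspected drug", with timing or a measured drug level, improvement on stopping or reducing the drug, and recurrence on re-exposure.
- **Probable:** a reaction with plausible timing "that follows a known or expected response pattern to the suspected study medication; that is confirmed by stopping or reducing the dosage", and with no other reasonable explanation.
- **Possible:** a reaction with plausible timing "that follows a known or expected response pattern to the suspected study medication; but that could readily be produced by a number of other factors".

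The grade Unlikely needs three things together: implausible timing, no known or suspected pattern, and an explanation in the patient's clinical state. Not Related is the residual: "Any event that does not meet the above criteria".

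The same section also defines a suspected adverse reaction by reasonable possibility, which "means there is evidence to suggest a causal relationship between the study medication and the AE". That definition has no pattern condition and is not mapped to the Table 3 grades.

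Relatedness is used in four other places:

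- In Table 4, for a death: "If unrelated Follow SAE timeline If related follow SUSAR timeline".
- In section 9.4, AEs still ongoing at the final visit that are possibly, probably or definitely "related or of other clinical significance must be followed for as long as necessary".
- In section 10.3.1, which tabulates TEAEs by relationship.
- In the secondary objectives (Synopsis, sections 2 and 7), which include SAEs attributable to the study drug.

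**The concern.** A causality scale has to be able to register a reaction nobody has seen before. This one cannot: without a recognised pattern the investigator has no related grade to give, and the residual row turns the gap into a positive statement of no relationship. The clinical experience in section 1.2 comes from healthy volunteers, primary biliary cirrhosis, and diabetes with fatty liver, so a reaction unfamiliar from those settings is a realistic prospect in alcoholic hepatitis.

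Three things are at stake:

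- **The safety record.** Section 9.2.2.1 makes the CRF the official record of AEs and SAEs, and the TEAE tables by relationship are part of the planned reporting.
- **Expedited reporting.** In Table 4 the ordinary SAE route reaches the monitoring board every 6 months and the FDA annually. The SUSAR route takes 2 working days and 7 or 15 days respectively.
- **The attributable-SAE secondary outcome,** if it is built on the site grade.

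**Working it through.** No sample-size or power figure is involved, so the check is one of logic. Code each row of Table 3 as a rule on seven yes/no features of an event:

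- T: reasonable temporal sequence
- L: drug level established in fluid or tissue
- K: known or expected response pattern
- D: improvement on stopping or reducing
- R: recurrence on re-exposure
- O: other factors could produce the event
- C: explained by the clinical state

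The rules, taking the highest grade met:

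- Definite = (T or L) and K and D and R
- Probable = T and K and D and not O
- Possible = T and K and O
- Unlikely = not T and not K and C
- Not Related = none of the above

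Seven features give 2^7 = 128 combinations, 64 with K and 64 without.

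| Pattern | Timing | Definite | Probable | Possible | Unlikely | Not Related |
|---|---|---|---|---|---|---|
| None known | plausible | 0 | 0 | 0 | 0 | 32 |
| None known | implausible | 0 | 0 | 0 | 16 | 16 |
| Known | plausible | 8 | 4 | 12 | 0 | 8 |
| Known | implausible | 4 | 0 | 0 | 0 | 28 |

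The counts show which cells the wording can reach. They are not frequencies of events.

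**Novel event.** Without a known pattern, 0 of 64 combinations reach a related grade, and all 32 with plausible timing are Not Related. That includes the event with plausible timing, measured drug level, positive dechallenge, positive rechallenge and no other cause. A novel event without plausible timing can be Unlikely instead (16 of 32).

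**Known-pattern event.** With plausible timing, 8 of 32 combinations are Not Related. These are the ones with D = no and O = no (L, R and C free, 2^3 = 8). Such an event fails Probable for want of dechallenge and fails Possible for want of a competing cause. A sudden death cannot show improvement on stopping. An unexplained one is therefore graded lower than one with competing explanations.

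**Against the other passages.** Reasonable possibility in section 9.1.3 asks only for evidence suggesting causality, and positive dechallenge and rechallenge are such evidence. So one event can be a suspected adverse reaction by the text and Not Related by the table. Section 9.2.2 relies on reactions that are suspected and also unexpected, yet Table 3 gives no related grade to an event that is unexpected in kind.

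**What the grade reaches.** It enters the CRF and the TEAE tables by relationship directly. It feeds the SUSAR decision, because section 9.2.2 asks for the investigator's causality judgment promptly to support regulatory reporting. It does not touch the primary SAE analysis in section 10.1, which counts patients with any SAE.

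**The case against.** A reader might infer that a novel toxicity drops out of the SUSAR pathway, and that the count of attributable SAEs of that kind must be zero. The documents do not support either.

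- **SUSAR status is not set by the site grade.** Under section 9.2.2 the study designated physician's causality assessment takes precedence, and that physician decides whether an SAE is an IND safety report under the FDA regulation. Table 3 is not cited there, and section 9.1.3 addresses it to the investigator.
- **The event still arrives promptly.** Every SAE goes to the coordinating unit and to NIAAA within 2 working days whatever its grade. The physician or the DSMC chair can call an ad-hoc committee meeting (section 10.6).
- **Attributable is undefined.** No passage says which grades, or whose assessment, count.
- **Follow-up is broader than relatedness.** Section 9.4 also covers events of other clinical significance, which a serious unexplained event would readily meet.
- **Terms are loose.** Response pattern is not defined, and the Unlikely row says known or suspected where the others say known or expected.

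The first four points stand and limit the consequences. The last does little: an event with plausible timing fails Unlikely on timing, however its pattern clause is read.

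The override also has limits. The physician is to consider a site assessment that the table has already pushed to the lowest grade. No passage says whether the physician may depart from Table 3. The aggregate-analysis safeguard in section 9.3 covers only the listed expected SAEs, so it does not help with a novel one.

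**Conclusion.** The defect in Table 3 is real at investigator level. Taken literally, no event of a kind new to the drug can be graded related, and every such event with plausible timing becomes Not Related. This conflicts with the plan's own definition of a suspected adverse reaction and with its suspected, unexpected concept. It distorts the relationship grades in the CRF and the TEAE tables.

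The gap between the SAE and SUSAR timelines in Table 4 is not an automatic delay. It applies only if the study designated physician leaves the site grade uncorrected; the fatality row works the same way, since Table 4 does not say whose view of relatedness counts. Expedited reporting of a novel reaction therefore rests on one person's correction. The attributable-SAE outcome is distorted only if it uses the site grade, which is not stated.

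The conclusion assumes that the conditions in each row are all required and that known pattern means a pattern already recognised for the drug. The known-pattern gap further assumes that competing factors are a requirement of Possible. If that clause is only a concession, those 8 combinations become Possible and the novel-event result is unchanged.

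**What to change.** Reconcile Table 3 with sections 9.1.3 and 9.2.2:

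1. Make the known or expected pattern supportive rather than required for the related grades, at least for Possible.
2. Define Not Related positively, for example by implausible timing or a clear alternative cause, not as the residual.
3. State that any event meeting the reasonable-possibility test is at least Possible. This also closes the gap for known-pattern events without dechallenge information.
4. State that the study designated physician's SUSAR decision uses the reasonable-possibility test, and whose assessment governs the fatality row of Table 4.
5. State which grades, and whose assessment, define an attributable SAE for the secondary outcome.

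The work is rewording one table, a few sentences and the CRF completion guide. The downside is somewhat more events rated Possible and a few more to assess for expedited reporting.
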